### 7.3.2 Dose Modifications and Dose Delays for Patients Experiencing Adverse Events during Expansion

For patients who do not tolerate the protocol-specified dosing schedule, dose reductions are permitted in order to allow the patient to continue treatment with enapotamab vedotin.

Specific instructions on dose interruptions and reductions for different toxicities are provided in [Table 2](#), [Table 3](#) and [Table 8](#). These instructions are applicable for both the 1Q3W and 3Q4W dosing schedules and should be applied in association with the relevant dose modification scheme described in [Table 4](#) to [Table 7](#).

**Table 2. Instructions for dose interruptions and reductions for enapotamab vedotin related hematologic toxicity occurring during a cycle**

Hematologic Toxicity	Enapotamab Vedotin Dose Modification
Grade 4 neutropenia (ANC < 0.5 x 10  /L) or Febrile neutropenia (fever ≥ 38.5 C and ANC < 1 x 10  /L)	Enapotamab vedotin dosing should be interrupted until recovery to ≤ grade 2.  G-CSF therapy should be initiated and/or maintained, if already started, at the discretion of the treating physician.  On Day 1 of the next cycle, the dose of enapotamab vedotin may be maintained if neutropenia was the only AE, G-CSF treatments are continued or if event has normalized to grade 0 or baseline. Otherwise, decrease by one dose level at the start of the next cycle (see Table 4 , Table 6 and Table 7 ).
Grade 3 afebrile neutropenia	Repeat CBC with differential count weekly, consider dose interruption until recovery to ≤ grade 2, and G-CSF prophylaxis in case of worsening or delayed recovery beyond 2 weeks.
Grade 4 thrombocytopenia	Enapotamab vedotin dosing should be interrupted.  Decrease by one dose level when dosing is resumed (see Table 4 , Table 6 and Table 7 ).  To restart enapotamab vedotin treatment following a dose interruption, the platelets count must be ≥ 50 x 10  /L.
Other enapotamab vedotin related AEs (excluding neutropenia, febrile neutropenia, and thrombocytopenia) ≥ Grade 3	Enapotamab vedotin dosing should be interrupted.  Decrease by one dose level when dosing is resumed (see Table 4 , Table 6 and Table 7 ).

Document Name: GCT1021-01 Protocol

Document Number: TMF-03326

Version: 11.0

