Nephritis and Renal dysfunction	Grade 1	Consider temporary hold pending consideration of baseline renal function and to confirm etiology 	Monitor for changes in creatinine levels. For $\geq$ Grade 2: If worsening or no improvement, consider administration of corticosteroids (prednisone 1-2 mg/kg or equivalent) followed by taper. Corticosteroid taper should be initiated upon immune-related AE improving to Grade 1 or less.
	Grade 2	Hold treatment until resolved to baseline 	
	Grade 3-4	Permanently discontinue	
Skin Toxicities	Grade 1-2	Continue treatment at the discretion of the investigator	Based on the severity of the adverse reaction, consider administration of corticosteroids. Corticosteroid taper should be initiated upon immune-related AE improving to Grade 1 or less.  For signs or symptoms of Steven Johnsons Syndrome (SJS) or Toxic Epidermal Necrolysis (TEN), withhold and refer the subjects for specialized care. If SJS or TEN is confirmed, permanently discontinue.
	Grade 3	Refer to text below	
	Grade 4	Permanently discontinue	
All other immune-related AEs	Grade 2	Continue treatment at the discretion of the investigator	Based on type and severity of AE, consider administration of corticosteroids. Permanently discontinue for any Grade 3 immune-related AE that recurs and for any life-threatening immune-related AEs.
	Grade 3	Refer to text below or discontinue based on the type of event.	
	Grade 4	Permanently discontinue	

1 20

Document Name: GCT1021-01 Protocol

Document Number: TMF-03326

Version: 11.0

---

[Redacted text block]

[Redacted text block]

[Redacted text block]

Document Name: GCT1021-01 Protocol

Document Number: TMF-03326

Version: 11.0

**Dose Delays**1Q3W and 3Q4W Schedule

For immune-related AEs, please refer to Section 7.3.3 regarding dose delays.

For all other AEs/Toxicities, enapotamab vedotin administration can be delayed for up to a maximum of 12 weeks. Radiological assessments should be continued during this period, as per protocol Section 8.4.7 and as clinically indicated, to monitor for disease progression.

Patients should be withdrawn from treatment if the treatment delay exceeds 12 weeks or if disease progression is observed while treatment is interrupted.

3Q4W Schedule Only

If a patient has to delay a dose for more than 14 days and the toxicity has resolved by that time, the patient should start with a new regular cycle upon resuming treatment.

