**Footnotes to Trial Flowchart – Expansion**

- 1 If the patient shows PD, is to start new anti-cancer treatment or withdraws from treatment due to another reason the End of treatment visit should be performed as soon as possible after decision of withdrawal.
- 2 The visit windows relate to the day of the previous visit. Visit 1 of Cycle 2 and onwards should be performed 7 days ±3 days after Day 15/22 of the previous cycle.
- 3 Signs, symptoms and diagnosis occurring between Visit 0 and first infusion should be recorded as medical history (see Section 8.4 for details). SAEs should be reported as of the signing of the informed consent.
- 4 Body weight will be measured on the first dosing day in a cycle, as part of the dose calculation. If body weight is assessed ≤ 7 days before the first day of the planned dosing in a cycle, this weight can be used to calculate dose and is the weight recorded in the eCRF.
- 5 Temperature, blood pressure and heart rate as according to Section 8.4.8.
- 6 All patients will have a CT-scan with contrast of thorax, abdomen, and pelvis performed as part of the screening procedure. If a CT-scan has been performed within 28 days prior to visit CIV1 as part of standard procedure, it is acceptable as screening CT-scan for the trial. If there is suggestion of brain metastases/tumors, a CT-scan of the head will be performed before inclusion. Clinical measurement in case of superficial cutaneous lesions should be performed within 28 days prior to visit CIV1 as part of standard procedure. For further details on imaging please refer to Section 8.4.7.
- 7 Radiological assessments and clinical measurements of superficial cutaneous lesions are to be performed every 6 (1Q3W and Cohort 8 3Q4W) or 8 (Cohort 6 3Q4W) weeks (±7days) from C1D1 until disease progression. If treatment is discontinued prematurely, prior to detection of disease progression (e.g., due to an adverse event), every effort should be made that scans continue according to the protocol until disease progression, start of a new anti-cancer treatment, withdrawal of consent or death (see Section 8.4.7 for details).
- 8 To be completed as indicated to confirm response or new symptoms at the end of treatment visit or at the physician discretion.
- 9 TSH, T3 and T4 will only be measured at screening and on Visit 1 of every even cycle.

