 - with end date of IMP defined as min (date of last IMP administration + 20 days, last contact date, date of death, cut-off date) For 1Q3W schedule
 - with end date of IMP defined as min (date of last IMP administration + 27 days (if D1 of cycle) or 20 days (if D8 of cycle) or 13 days (if D15 of cycle), last contact date, date of death, cut-off date) For 3Q4W schedule
- Actual cumulative dose (mg): sum of all actual doses administered.
- Planned cumulative dose (mg) only used for calculation of relative dose intensity:
 Allocated dose level * weight in kg * number of cycles initiated for 1Q3W and allocated
 dose level * weight in kg * 3 * number of cycles initiated for 3Q4W. For subjects whose
 body mass index (BMI) is greater than 30 kg/m2, the formula should use a weight
 that, based on the subject's height, corresponds to a maximum BMI of 30. When a
 cycle is missed/skipped, this cycle is also included to count the number of cycles
 initiated.
- Dose intensity (mg/cycle): actual cumulative dose in mg divided by the number of cycles initiated.
- Relative dose intensity (%): 100 * ratio of actual cumulative dose and planned cumulative dose.
- Number of days in trial: max (last contact date, date of death) date of first IMP administration + 1.

Page 13 of 46

TPL N°: eTPL SA-02-01 Of SOP SA-02.08 TPL Effective Date: 31 Mar 2016 Genmab - GCT1021-01 Version: 4.0

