17.1 Extent of Exposure

For the expansion part, the number of doses received, the duration of exposure to enapotamab vedotin (days), the actual cumulative dose (mg), as well as the actual and relative dose intensities (continuous and in categories: >= 110%, 90% to < 110%, 70% to < 90%, 50% to < 70%, < 50%, missing) will be summarized by means of descriptive statistics using the safety set.

Version: 4.0

The duration of exposure to enapotamab vedotin (days) will also be presented by a Kaplan-Meier plot (without censoring).

Also, the number of subject days (total number of days in trial) will be presented by means of descriptive statistics for each dose/cohort group.

For the dose-escalation part, only the number of doses received, number of days in the trial and the duration of exposure will be presented as mentioned above.

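### Relative dose intensity is counted per cycle started, not per unit time, so short holds (under one cycle, or up to 14 days mid-cycle on 3Q4W) leave it unchanged

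*SAP*

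**What the plan says.** SAP 4.6 defines "Relative dose intensity (%): 100 * ratio of actual cumulative dose and planned cumulative dose". Actual cumulative dose is the milligrams given, whatever the dates. Planned cumulative dose is allocated dose level × weight × cycles initiated, with a further factor of 3 on 3Q4W and weight capped at a BMI of 30. The companion measure is on the same scale: "Dose intensity (mg/cycle): actual cumulative dose in mg divided by the number of cycles initiated". The one allowance for lost time is that when a "cycle is missed/skipped, this cycle is also included to count the number of cycles" initiated.

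SAP 17.1 summarises relative dose intensity for the expansion part, both as a continuous value and in bands: 110% or more, "90% to < 110%, 70% to < 90%, 50% to < 70"%, below 50%, and missing.

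The protocol allows holds. In the *Dose Delays* text that follows Table 8 in Section 7.3.3, for toxicities other than immune-related ones, "enapotamab vedotin administration can be delayed for up to a maximum of 12 weeks". For 3Q4W only, "If a patient has to delay a dose for more than 14 days and the toxicity has resolved by that time", treatment resumes with a new cycle. That a shorter delay continues the same cycle is implied, not stated. Table 2 in Section 7.3.2 interrupts dosing for Grade 4 or febrile neutropenia and then says that "the dose of enapotamab vedotin may be maintained if neutropenia was the only AE", with further conditions given there.

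**The concern.** A reader of a banded relative dose intensity will usually take it as the fraction of the intended dose rate that was delivered. Here it is the fraction of the intended dose per cycle started. If a hold ends with the full dose and no dose is lost, numerator and denominator are the same as if there had been no hold. A patient held repeatedly for toxicity can then sit in the same band as one dosed on schedule.

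The schedules are also treated differently. On 3Q4W, a mid-cycle hold of more than 14 days abandons the rest of the cycle, and the undelivered doses stay in the denominator. On 1Q3W, a hold of the same length leaves no trace. Cohorts 2 and 8 enrol the same population on the two schedules, and SAP Section 4 puts them on one page. What is at stake is the tolerability description and that side-by-side reading.

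**Working it through.** The documents report no relative dose intensity value, so there is no figure to reproduce. They also give no cycle counts or hold frequency, so the cycle counts below are assumptions. Weight is taken as constant and cancels.

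**Formulas**

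- SAP ratio: full doses given ÷ (doses per cycle × cycles initiated).
- Time-based ratio: full doses given ÷ (planned doses per day × days). Planned doses per day are 1/21 (1Q3W) or 3/28 (3Q4W). Days run from first dose to last dose + 20 (1Q3W), or last dose + 27, 20 or 13 when the last dose is on Day 1, 8 or 15 (3Q4W), counted inclusively. These tails come from the SAP's duration-of-exposure definition, without its truncation.

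**Check with no delay.** Six 1Q3W cycles: 105 + 20 + 1 = 126 days, and 126/21 = 6 planned doses. Four 3Q4W cycles: 98 + 13 + 1 = 112 days, and 112 × 3/28 = 12 planned doses. Both measures give 100%.

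**Holds that leave the SAP ratio at 100%** (full-dose resumption, no omitted dose)

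| Case | Time-based |
|---|---|
| 1Q3W, one 14-day delay, 2 cycles | 42/56 = 75.0% |
| same, 4 cycles | 84/98 = 85.7% |
| same, 6 cycles | 126/140 = 90.0% |
| same, 8 cycles | 168/182 = 92.3% |
| 1Q3W, 6 cycles, 14 days before each of cycles 2–6 | 126/196 = 64.3% |
| 3Q4W, one 14-day delay, 4 cycles | 112/126 = 88.9% |

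Against the SAP bands, the single 1Q3W delay changes the band at 2 and 4 cycles but not at 6 or 8. The repeated delay falls two bands.

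**One 15-day hold in 4 cycles, by schedule**

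| Case | SAP ratio | Time-based |
|---|---|---|
| 1Q3W | 4/4 = 100% | 84/99 = 84.8% |
| 3Q4W, held at Day 8, new cycle | 10/12 = 83.3% | 10/(106 × 3/28) = 88.1% |
| 3Q4W, held at Day 15, new cycle | 11/12 = 91.7% | 11/(113 × 3/28) = 90.9% |

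The abandoned 3Q4W cycle lasts 7 + 15 = 22 or 14 + 15 = 29 days, which gives 84 + 22 = 106 and 84 + 29 = 113 days.

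**What the SAP ratio does show.** Dose reductions show. So does one omitted weekly dose in 4 cycles (11/12 = 91.7% on both measures), and so does stopping 3Q4W in Cycle 1 after Day 1 or Day 8 (33.3% or 66.7% on both).

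**Noise in the time-based measure.** Table 11, footnote 2 states: "The visit windows relate to the day of the previous visit". Windows can therefore accumulate. With only the 3 late days that this footnote allows at each new cycle, a 1Q3W patient with no hold would read 42/45 = 93.3% at 2 cycles and 168/189 = 88.9% at 8. If one late day at each of Days 8 and 15 is added (5 per cycle; taken from the escalation schedule in Table 9, because the Table 11 window row is broken in the available text), the values are 42/47 = 89.4% and 168/203 = 82.8%.

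**The case against.** The strongest reply is that the SAP is open about its unit, milligrams per cycle, and that delays are reported elsewhere. SAP 17.1 gives number of doses, cumulative dose and duration of exposure. SAP 17.2 tabulates events leading to interruption and to dose reduction, and the exposure listing covers adjustments and interruptions. All of this stands. A delay can be recovered for a patient, and the gap is only that no tabulated quantity combines dose with time.

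It can also be said that the full-dose route is narrow. Table 2 sets conditions after Grade 4 or febrile neutropenia, and resuming on Day 1 of the next cycle may involve no delay at all. Tables 2 and 3 require reductions for several other toxicities, and those do show in the ratio. This limits how often the blind spot arises but does not close it. In Table 2, the Grade 3 afebrile neutropenia row has interruption to be considered and states no reduction. In Table 8, some Grade 3 hepatic elevations lead to a hold and then resumption if resolved within 14 days, again with no reduction stated there.

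A time-based value has a fault of its own, because permitted visit windows move it with no hold. That is a reason to add it beside the present ratio and not to replace the ratio.

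A reader might infer more: that a 3Q4W Day 1 delay of any length is invisible, or that the value for long delays is arbitrary because no day count makes a cycle missed or skipped. The documents do not support either. The missed-cycle clause covers both schedules, so a delay of a full cycle or longer can lower the ratio. The dose-modification text in Section 7.3.1, Tables 4 to 7 and next to *Dose Delays* is partly redacted, so a rule that cannot be seen there cannot be called missing.

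**Conclusion.** The point holds within limits. With full-dose resumption and no omitted dose, three kinds of hold leave the SAP ratio unchanged: a 1Q3W delay shorter than 21 days, a 3Q4W Day 1 delay shorter than 28 days, and a 3Q4W mid-cycle delay of 14 days or less. In the examples worked here, time-based values run from 64.3% to 92.3% while the SAP ratio stays at 100%. For a 15-day hold in one of 4 cycles, the SAP ratio reads 100% on 1Q3W and 83.3% or 91.7% on 3Q4W.

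This rests on assumed cycle counts, on reading a missed cycle as a whole cycle lost, and on the implied rule that a 3Q4W delay of 14 days or less resumes the same cycle. A reading of exactly 100% also needs stable weight and a complete last cycle. Protocol 8.4.4 re-measures weight at Visit 1 of each cycle, and SAP 4.6 does not say which weight enters the planned dose. The safer statement is that the hold does not change the ratio.

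The severity is minor. A reader might infer that toxicity-driven delays are hidden or that a safety conclusion would change. Neither follows: the measure is descriptive, no endpoint or test uses it, and the other exposure outputs show delays.

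**What to change.** Keep the present ratio and label it *relative dose per cycle started*. Add one row to the expansion exposure table in SAP 17.1:

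Time-based relative dose intensity (%) = 100 × actual cumulative dose ÷ (allocated dose × weight × rate × days), with rate 1/21 for 1Q3W or 3/28 for 3Q4W, and days from first dose to last dose + 20 for 1Q3W, or last dose + 27, 20 or 13 for 3Q4W when the last dose is on Day 1, 8 or 15, counted inclusively.

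- Use the same BMI-capped weight as the present ratio.
- Do not truncate the days at death, last contact or cut-off. One full 1Q3W dose followed by death on day 10 would give (1/10)/(1/21) = 210% instead of 100%.
- Footnote that scheduling within the permitted visit windows also moves the value, so a figure just below 90% is not by itself evidence of a hold.

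I would not add a day count for missed or skipped cycles here. The related protocol text is partly redacted, and a simple count can charge an abandoned 3Q4W cycle twice, once for its undelivered doses and again as a skipped cycle.

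The cost is one derived variable from dates already collected, one relabelled row, one new row and a footnote. Data to the 22 March 2021 cut-off are already in the CSR and the SAP addendum repeats no exposure table, so this would be a supplementary output. The addendum does rerun all derived-dataset programs on the whole database, which keeps the extra work small. The remaining weaknesses are the visit-window noise and that a hold ending in discontinuation is still not captured.

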4.7 Partial/Missing Dates

Partial or missing dates in general will not be imputed (medical history, previous cancer treatment).

For the calculation of the time (in months) from initial diagnosis of primary site to date of first IMP administration and time (in months) since most recent recurrence/relapse or progression to date of first IMP administration, the following imputation rules will be applied when the date of first diagnosis or date of most recent recurrence/relapse or progression is incomplete:

- If the day is missing: first day of the month
- If the day and month are missing: first day of July.
- If the day and month are missing and if the year is the same as the year of first IMP administration: leave missing.

For the assignment to prior or concomitant medication the following rules will be applied in case of incomplete or missing dates:

- If medication is ongoing or end date is missing then medication will be considered as concomitant and missing date(s) will not be imputed.
- If end date is incomplete: if the day is missing: the end date will be imputed with the last day of the month; if the day and month are missing: the end date will be imputed with min(31 December of the year, last contact date, date of death).

The imputed dates will only be used for the assignment to prior or concomitant and will not be used in any other calculation and will not be listed.

For new anti-cancer therapy, when the start date is partial or missing, the date will be imputed:

Page 14 of 46

TPL N°: eTPL SA-02-01 Of SOP SA-02.08 TPL Effective Date: 31 Mar 2016 TPL Version: 02

- If start date is missing, but end date is not missing: the start date will be set to the end date.
- If start date remains missing, the start date will be set to the minimum of (last contact date and date of death).
- If start date is incomplete: if the day is missing: the start date will be imputed with the last day of the month; if the day and month are missing: the start date will be imputed with min (31 December of the year, the last contact date, date of death, end date if not missing).

The imputed dates will only be used to define the start of the new anti-cancer therapy for progression free survival and will not be used in any other calculation and will not be listed.

For the assignment of adverse events (AE) the following rules will be applied in case of missing or incomplete start date:

- If end date is before the date of first IMP administration, the adverse event will be assigned to the pre-treatment period (reported with medical history) and the start date will remain missing/incomplete;
- If start date is missing and end date is after or on the date of first IMP administration or the end date is missing, the start date will be imputed by the date of first IMP administration;
- If start date is incomplete and end date is after or on the date of first IMP administration or the end date is missing, the start date will be imputed as follows:
 - If the day is missing and if the start date and date of first IMP administration share the same month and year, the missing start day will be imputed as the day of first IMP administration. If the start date month is after the month of first IMP administration, day will be imputed as the first (i.e. 01-MMM-YY);
 - If the day and month are missing and if the start date and date of first IMP administration share the same year, day and month will be imputed as the day and month of first IMP administration. If the start date year is after the year of first IMP administration, the month and day will be imputed as January first (i.e. 01-JAN-YY).

The imputed date will only be used for the assignment of the treatment-emergent adverse event flag/trial periods and will not be used in any other calculation (unless specified otherwise) and will not be listed.

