15.1.4 Progression-Free Survival according to RECIST 1.1

PFS is defined as the number of days from the date of first IMP administration to first PD or death whichever occurs first.

PFS will be derived for all subjects and presented graphically as well as summarized using survival analysis methods:

- Kaplan-Meier curves
- Kaplan-Meier curves by subgroups defined for cohorts 2 and 8 and for cohort 6 as mentioned in section 4.4
- Kaplan-Meier estimates.
- Kaplan-Meier estimates by subgroups defined for cohorts 2 and 8 and for cohort 6 as mentioned in section 4.4.

PFS will be censored in accordance with Table A in Appendix 3 in the FDA Guidance for Industry "Clinical Trial Endpoints for the Approval of Cancer Drugs and Biologics (2007)".In summary, PFS will be censored if no event (progression or death) is observed before the first of (i) the analysis cut-off date, and (ii) the date when a new anti-cancer therapy is started. The censoring date will be the date of the last adequate tumor assessment prior to cut-off/start of new anti-cancer therapy. In case of an event after 2 or more missed scans, censoring will be done at last adequate tumor assessment date before the missed scans (Censoring rule based on FDA guideline). Two scans are considered missing if no evaluable response result (CR, PR, SD or PD) is available within a period of 98 days (6+1 weeks times 2) for 1Q3W dose schedule and a period of 126 days (8+1 weeks times 2) for 3Q4W dose schedule.

[figure not shown]

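### A new-therapy start date lacking only its day is set to month-end without the cap given to vaguer dates, so it can fall after the therapy's own end or after death and turn a censored patient into a PFS event

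*SAP*

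**What the plan says.** SAP 4.7 has four branches for a partial or missing start of new anti-cancer therapy.

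1. Start wholly missing, end known: "If start date is missing, but end date is not missing: the start date will be set to the end date".
2. Start still missing: "the start date will be set to the minimum of (last contact date and date of death").
3. Day and month both unknown: "the start date will be imputed with min (31 December of the year, the last contact date, date of death, end date if not missing").
4. Only the day missing: "if the day is missing: the start date will be imputed with the last day of the month; if the day and month are missing" (its closing words introduce branch 3). No bound follows the month-end value.

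The same section states the purpose of the date: "The imputed dates will only be used to define the start of the new anti-cancer therapy for progression free survival". It adds that imputed dates serve no other calculation and are not listed.

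SAP 15.1.4 is where the date takes effect: "PFS will be censored if no event (progression or death) is observed before the first of (i) the analysis cut-off date". Its second limit is given as "ii) the date when a new anti-cancer therapy is started". A censored patient is censored at the last adequate tumor assessment before that point. Section 3.2 of the SAP addendum keeps the PFS method unchanged, and its section 2.1 reuses the programs and decision rules, so the rule carries into the addendum analysis. I found no cap or consistency check on this date elsewhere in the protocol, SAP or addendum.

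**The concern.** Branches 1 to 3 never put the start after a known end date, and branches 2 and 3 also respect last contact and death. Branch 4 has the most information, yet it alone can place the start after the therapy has ended or the patient has died. No reason is given for bounding the vaguer date and not the clearer one.

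The date decides whether a progression or death came before the new therapy. An imputed start later than the true start could possibly be turns an observation that SAP 15.1.4 means to censor into an event. Two patients with the same history can then be handled in opposite ways, and the one whose date is better documented gets the wrong result. Because imputed dates are not listed, a reader of the listings could not see it.

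**Working it through.** The plan gives no figure on this point, so there is nothing to reproduce. The check applies the two sections to illustrative records.

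**Inputs.** The imputation branches come from SAP 4.7 and the censoring rule from SAP 15.1.4. *Before* is read strictly, so an event on the start date is not before it. All dates fall in 2020, ahead of the 22 March 2021 data cut-off in SAP addendum 2.1, so only the new-therapy limb matters. Last contact is taken to be later than the progression in A, C and D, and equal to the date of death in B.

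**Formulas.**
- Current rule: S = last day of the recorded month.
- Capped rule: S = min(last day of the month, therapy end if known, last contact, death).
- Status: event if the event date < S, otherwise censored.

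| Record (start recorded as March 2020) | Current S | Status | Capped S | Status |
|---|---|---|---|---|
| A. Therapy ended 5 March, PD 20 March | 31 March | event | 5 March | censored |
| B. Death 12 March | 31 March | event | 12 March | censored (strict reading) |
| C. True start 3 March, therapy ongoing, PD 20 March | 31 March | event | 31 March | event |
| D. True start 3 March, therapy ended 10 March, PD 8 March | 31 March | event | 10 March | event |

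**Impossible dates.** In A the imputed start is 31 − 5 = 26 days after the therapy's own end. In B it is 31 − 12 = 19 days after death.

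**Less information, better answer.** If A had only the year, branch 3 gives min(31 December, last contact, 5 March) = 5 March, and the patient is censored. If A had no start date at all, branch 1 gives 5 March and again censors. Only the record with a known month is called an event.

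**What the cap leaves alone.** In C and D the true start of 3 March would censor, yet both stay events under the cap. The cause there is the choice of the latest possible date, not the missing bound.

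**Size of the month-end convention, for scale.** Over 2020, month-end minus true start runs from 0 to 30 days. The shifts sum to 7×465 + 4×435 + 406 = 5,401, and 5,401/366 = 14.8 days on average if every day is equally likely. Suppose an event falls with equal chance on each of the K days after the true start. It stays a PFS event when it falls fewer days after the start than the shift. The mean count of such days is (5,401 − 354)/366 = 13.79, so the share is 13.79/K: 46% for K = 30, 33% for 42, 25% for 56 and 14% for 98. These shares describe the convention as a whole, in day-missing patients who have such an event. The part due to the missing cap is smaller and cannot be computed from the documents.

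**The case against.** The best counter-argument is that very few patients can be affected and little depends on them.

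- A patient who progresses and then changes drug already has a PFS event, so the imputed date is irrelevant.
- After stopping without progression, Protocol 8.4.7 asks for scans only until progression, new treatment, withdrawal of consent or death. A progression scan after the new drug, as in A, is off schedule.
- Events after two or more missed scans (98 days for 1Q3W, 126 for 3Q4W) are censored anyway.
- New treatment is also asked about at the 30-day safety visit (Protocol 5.6.5), and follow-up contacts ask for start and stop dates (5.6.6). Nothing in the documents shows that missing days are common.
- PFS is secondary, summarized by Kaplan-Meier, with no control arm and no PFS test. The error adds events, so it does not flatter the drug.

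All of this stands and limits the importance. None of it explains why the clearer date goes unbounded.

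A reader might also infer that the missing cap is why events under the next drug are counted as PFS events in general, or that every patient with a day-missing start and a later event in that month changes status. Records C and D show otherwise. A reader might extend the effect to duration of response, because SAP 15.1.6 borrows the PFS censoring rules. But SAP 4.7 confines the imputed date to PFS, so the effect on duration of response is undefined rather than shown.

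**Conclusion.** The point holds as an inconsistency between two branches of one rule, and the rule as written can give a wrong PFS status. It does so when only the day is missing and either progression falls on or after the therapy's known end date but before month-end, or the patient dies in the start month before its last day. An event dated on last contact behaves like a death. The progression case in A needs no view on ties. The death case needs *before* to exclude the same day.

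Each such record becomes an event at the event date instead of being censored at the last adequate assessment. The imputed start is never more than 30 days after the true one. The number of such records is not in the documents and is probably small, so the effect on the PFS estimates is likely minor. The conclusion rests on the text of SAP 4.7 and 15.1.4 as written and assumes that no unstated programming check corrects the date.

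**What to change.** In SAP 4.7, replace the day-missing rule with: min(last day of the month, therapy end date if not missing, last contact date, date of death). Add that an event dated on the imputed start is not before it. Each bound is a date that the true start cannot exceed if the recorded dates are consistent, so the cap adds no assumption.

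In the same edit, say whether the imputed date also applies to duration of response, since SAP 4.7 and 15.1.6 point in different directions.

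The cost is one clause, one line of code and a sentence on each of the two clarifications. If the month-end convention itself is a worry, an optional sensitivity analysis could use the first of the month, but not before first dose. That errs the other way: a progression on 10 March before a true start of 20 March would be censored.
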